5.5. Analysis Populations

5.5.1. Intent-to-Treat Population

The intent-to-treat (ITT) population will be defined as all randomized subjects who received at least one dose of IP. This ITT population will be used for the primary efficacy analysis. Subjects will be included in the treatment group to which they are randomized.

5.5.2. Safety Population

The safety population will include all randomized subjects who received at least one dose of IP. The analysis of safety data in this study will be based on the safety population and subjects will be included in the treatment group to which they actually received.

5.5.3. Per-Protocol Population

The per protocol (PP) population will include all randomized subjects who received at least one dose of IP, have a baseline and at least one post-baseline oral ulcer evaluation, and have no important protocol violations during the 12-week Placebo-controlled Treatment Phase. The final determination of important protocol violation criteria will be made prior to the unblinding of the database and will be documented separately.

5.5.4. Apremilast Subjects as Treated Population

Safety analyses for the apremilast-exposure period will be based on the apremilast subjects as treated population, which will include all subjects who actually receive 30 mg BID at the randomization visit or switched (at the Week 12 visit) to the APR 30 BID. Subjects will be included in the treatment sequence they actually received.

6. SUBJECT DISPOSITION

The number of subjects screened, the number and percentage of subjects randomized and not randomized among all subjects screened, and the reasons for not being randomized will be summarized. The above percentages will be calculated using the number of subjects screened as the denominator.

The number and percentage of subjects who entered, completed, and discontinued each study phase (Placebo-controlled Treatment Phase, Active Treatment Phase, and Observational Follow-up Phase), and the number and percentage of primary reasons for discontinuation of each study phase (except for the Observational Follow-up Phase) will be summarized by treatment group at randomization. For the Placebo-controlled Treatment Phase, the summary of the number and percentage of subjects who completed and entered or completed but did not enter the Active Treatment Phase will be provided separately.

The primary reasons for discontinuation are collected in the Discontinuation eCRF and will be summarized with the following categories:

- Adverse event
- Lack of efficacy
- Non-compliance with IP
- Withdrawn by subject
- Death
- Lost to follow-up
- Study terminated by sponsor
- Protocol violation
- Pregnancy
- Other

The number of subjects randomized, and the number and percentage of subjects included in the ITT, PP, Safety and Apremilast as Treated analysis populations will be summarized by treatment group (placebo and 30 mg BID) at randomization. The percentages will be based on the number of subjects randomized. A listing of subject eligibility/analysis population and a listing of subjects who discontinue the study early and reasons for discontinuation will be provided. A listing of subjects excluded from the per protocol population, with the reasons for exclusions, will also be provided.

The number and percentage of subjects by region, country, study site and treatment group will be tabulated based on the ITT population.

Subject disposition for the optional Open-label Extension Phase will be presented in a separate listing.

7. PROTOCOL DEVIATIONS/VIOLATIONS

The protocol deviations/violations will be identified and assessed by clinical research physician or designee following company standard operational procedure.

The number and percentage of protocol violations and deviations will be summarized for the ITT population from Weeks 0 to 12 by treatment group at randomization, and after Week 12 by treatment sequence and the total for subjects who enter the Active Treatment Phase.

A listing of subjects with protocol deviations/violations in the ITT population will be provided.

CELGENE PROPRIETARY INFORMATION

8. DEMOGRAPHICS AND BASELINE CHARACTERISTICS

The demographics and baseline characteristics will be summarized for the ITT population. The demographics and baseline clinical characteristics will also be summarized for subjects who discontinued study early within the ITT population. Individual subject listings will be provided to support the summary tables.

8.1. Demographics

Summary statistics will be provided by treatment group for the following continuous variables:

- Age (years)
- Weight (kg)
- Height (cm)
- Body mass index (BMI; kg/m²)

Number and percentage will be provided by treatment group for the following categorical variables:

- Age category (< 65, ≥ 65 years; < 40, ≥ 40 to < 65, ≥ 65 years)
- Sex (female, male)
- Race (American Indian or Alaska Native, Asian, Black or African American, Native Hawaiian or Other Pacific Islanders, White, Other)
- Ethnicity (Hispanic or Latino, not Hispanic or Latino)
- Region (Japan, Other; Europe, North America, Asia, Rest of the World)
- Weight category (< 50, ≥ 50 to 60, ≥ 60 to 70, ≥ 70 to < 85, ≥ 85 kg)
- BMI category (< 18.5, ≥ 18.5 to < 25, ≥ 25 to < 30, ≥ 30 kg/m²)

The body mass index (BMI) will be calculated as

BMI (kg/m²) = baseline weight (in kilograms) / height² (in meters).

- Alcoholic beverage intake (yes [<1 drink per week, 1-14 drinks per week, >14 drinks per week], no)
- Tobacco use (current user, past user, non-user).

8.2. Baseline Disease Characteristics

Variables indicated below will be summarized descriptively:

- Duration of disease (time [in years] from first diagnosis to the informed consent date)
- Duration of disease (≤ 2, > 2 to ≤ 6, > 6 to ≤ 10, > 10 years)
- History of uveitis from IRT data

- History of uveitis from clinical data, defined as having a history of 'Anterior uveitis, iridocyclitis', 'Cells in vitreous', 'Chorioretinitis, retinovasculitis', and/or 'Posterior uveitis', which are collected on screening and randomization visit BD manifestation activity history
- Behçet's syndrome diagnostic criteria
- Ophthalmologic examination for presence of uveitis
- Chest Radiograph (Normal, Abnormal [Not Clinically Significant, Clinically Significant])
- Electrocardiogram (ECG) (Normal, Abnormal [Not Clinically Significant, Clinically Significant])
- Baseline BD activities as measured by number of oral ulcers, number of genital ulcers (non-zero for subjects who had genital ulcers at baseline), pain of oral ulcers as measured by VAS, pain of genital ulcers as measured by VAS (non-zero), BD Current Activity Index score, BD QOL total score, BSAS score, total score of PGA of BD skin lesions (non-zero),

• Baseline oral ulcers category (≥ 2 to ≤ 5 , > 5 to ≤ 10 , > 10)
- Prior use of immunosuppressants (Yes, No)
- Prior use of colchicines (Yes, No)
- Prior use of oral corticosteroids (Yes, No)
- Prior use of topical corticosteroids (Yes, No)
- Prior use of biologics (Yes, No)
- Prior use of NSAIDs (Yes, No)
- Prior use of analgesics/anesthetics (Different from NSAIDs) (Yes, No)

8.3. Medical History

Medical history will be coded according to Medical Drug Regulatory Activities (MedDRA). A frequency summary table of medical history will be presented by treatment group, system organ class (SOC) and preferred term (PT).

8.4. Prior Therapy

Prior medications are defined as therapies that were started before the start of the study treatment (whether or not ended before the start of the study treatment). Prior therapies that continue into study treatment period(s) will be also reported as concomitant medications. The Anatomical Therapeutic Chemical (ATC) coding scheme of the World Health Organization Drug Dictionary (WHODD) will be used to group medications into relevant categories. A frequency summary of prior medications will be provided by treatment group, ATC1 level, and standardized medication name.

8.5. Concomitant Medications and Procedures

Concomitant medications/procedures are defined as non-study medications or procedures that are started after the start but before the end of the study treatment (of each study period), or started before the start of the study treatment and ended or remain ongoing during the study treatment.

All concomitant treatments documented during the placebo-controlled period and apremilast-exposure period will be summarized respectively in frequency tabulations. The Anatomical Therapeutic Chemical (ATC) coding scheme of the WHODD will be used to group medications into relevant categories. A frequency summary of concomitant medications for each analysis period will be provided by treatment group, ATC1 level, and standardized medication name. Concomitant medications in the Posttreatment Observational Follow-up Phase will be summarized for all subjects who enter the phase. In addition, concomitant medications initiated in the Posttreatment Observational Follow-up Phase will be summarized separately and a corresponding listing will be provided.

A frequency summary table for concomitant procedures will be presented for each analysis period by presented by treatment group, MedDRA SOC, and PT.

CELGENE PROPRIETARY INFORMATION

9. STUDY TREATMENTS AND EXTENT OF EXPOSURE

9.1. Treatment Duration

Treatment duration will be summarized by treatment group for the placebo-controlled period using the safety population, and for the apremilast-exposure period using the apremilast subjects as treated population. Subjects whose treatments are switched to active therapy will have the following treatment group designation: Placebo/APR 30 BID in the apremilast-exposure period. A subject data listing of study drug administration will be provided.

Treatment duration (in weeks) is calculated as (the date of the last dose of IP – the date of the first dose of IP + 1) / 7 during each period and rounded to one decimal place. Summary statistics for subject years, treatment duration (in weeks), as well as a frequency summary of treatment duration categories (e.g., \geq 1 day, < 2 weeks, \geq 2 to < 6 weeks, etc.), will be provided.

The specific definitions of the first and last dose dates for the Placebo-controlled and Apremilast-exposure periods are given below:

- Placebo-controlled period:
 - First dose date: The date of the first dose of IP.
 - Last dose date:
 - 1 day before the date of first dose of apremilast administered at the Week 12/Visit 9, or
 - The date of the last dose of IP in the study for subjects who discontinue the study on or prior to Week 12/Visit 9.
- Apremilast-exposure period:
 - First dose:
 - The date the first dose of apremilast is administered for subjects who receive apremilast at randomization, or
 - The date the first dose of apremilast is administered at the Week 12 (Visit 9) for subjects who originally received placebo during the Placebo-controlled Treatment Phase and switched to the APR 30 BID group when entering Active Treatment Phase.
 - Last dose date:
 - The date of the last dose of apremilast during Active Treatment Phase for subjects who have either completed or discontinued Active Treatment Phase by the time of database lock or study close, or
 - The latest date out of scheduled visit dates, AE event dates or study drug administration dates for treatment ongoing subjects at time of database lock (ie, the second database in Section 2).

9.2. Treatment Compliance

Subjects are instructed to return the IP blister cards, including any unused IP, to the study site at each post-baseline visit for pill counts and reconciliation. The number of tablets dispensed and returned will be recorded at visits specified in the Table of Events, Table 1 in the protocol.

The compliance rate (%) will be calculated for each subject as 100 times the total number of tablets taken (total number of tablets dispensed minus the total number of tablets returned) over the period divided by the intended total number of tablets that should have been taken over the same period.

It is assumed that from the first dose date through the last dose date, a subject takes the first 3 rows of tablets (6 tablets per row/day) on each complete blister card before taking the remaining rows (4 tablets per row/day), and completes all 33 rows and then starts a new blister card if multiple cards are dispensed. It is also assumed that a subject takes the full day's tablets from a new blister card on a study drug dispense date.

The intended total number of tablets is calculated as follows. First order the first dose date, the second dispense date, the third dispense date, etc., and the last dose date. The first and last dose dates are defined in the same way as those defined for treatment duration calculations. The intended number of tablets between any 2 consecutive dates is calculated as

$$4 \times n + 2 \times \text{int}[(n + 32) / 33] + 2 \times \text{int}[(n + 31) / 33] + 2 \times \text{int}[(n + 30) / 33],$$

where n denotes the number of days between the 2 consecutive dates (i.e., the second date minus the first date for all pairs of consecutive dates, and the second date minus the first date plus 1 for the last pair), and “*int*” denotes the integer part of the result. Then the intended total number of tablets is the sum of all intended numbers of tablets as calculated above from the first dose date through the last dose date.

Of note, compliance rate will not be calculated for subjects (if existent) who have only the dispense record at Week 0/Visit 2 and no other drug accountability records.

Compliance will be summarized using descriptive statistics for the placebo-controlled period and apremilast-exposure period. The acceptable range for compliance is defined as between 75%-120%. The number and percentage of subjects will be summarized by category < 75%, \geq 75% to \leq 120%, and > 120%.

A subject data listing of drug accountability records will be provided.

10. EFFICACY ANALYSIS

10.1. General Approaches to Efficacy Analyses

The efficacy analyses will be based on the ITT population, and analyses of the primary efficacy endpoint will also be provided using the PP population. Statistical comparisons will be made between the apremilast group and the placebo group using 2-sided tests and the overall significance level will be maintained at 0.05.

All efficacy endpoints will be summarized by time points per the report conventions in Section 5.1. Analyses of the primary endpoint, secondary [REDACTED] endpoints assessed during the Placebo-controlled Period will be presented by randomized treatment group, Placebo and 30 mg BID. During the Active Treatment Phase, data will be presented by treatment sequence, i.e., Placebo/30 mg BID, or 30 mg BID/30 mg BID.

Efficacy results that will be considered statistically significant are described in Section 10.2.1. All statistical tests will be conducted at the $\alpha = 0.05$ (2-sided) level, and 2-sided p-values will be reported.

10.2. Efficacy Evaluation for the Double-blind, Placebo-controlled Treatment Phase

10.2.1. Multiplicity

Planned statistical tests will be conducted between APR 30 BID and placebo for the primary endpoint, and selected secondary endpoints evaluated at Week 12.

The multiplicity of the analyses of the primary and selected secondary efficacy endpoints will be adjusted using a gatekeeping Procedure. This procedure will preserve the Family Wise Error Rate of the multiple analyses. The analyses will be performed in sequence until one of the analyses has failed to show the significant difference or all analyses have been completed at a significance level of 0.05. The sequence of the analyses for the selected secondary efficacy endpoints are listed below:

Table 4: Rank of the Endpoints (Including Primary Efficacy Endpoint) in the Hierarchy of Multiplicity Adjustment

| Endpoints | Rank of Endpoints in Multiple Testing Sequence |
|---|--|
| AUC for the number of oral ulcers from baseline through Week 12 | 1 |
| Change from baseline in the pain of oral ulcers as measured by VAS at Week 12 | 2 |
| Change from baseline in Behçet's Syndrome Activity Score (BSAS) at Week 12 | 3 |
| Change from baseline in disease activity as measured by Behçet's Disease Current Activity scores (BD Current Activity Form) at Week 12 | 4 |
| Proportion of subjects achieving an oral ulcer complete response (oral ulcer-free) by Week 6, after start of dosing, and who remain oral ulcer free for at least 6 additional weeks during the 12-week Placebo-controlled Treatment Phase | 5 |
| Time to oral ulcer resolution (complete response), ie, the first instance when a subject has a complete response, during the Placebo-controlled Treatment Phase | 6 |
| Complete response rate for oral ulcers at Week 12 | 7 |
| Change from baseline in the BD QoL score at Week 12 | 8 |
| Complete response rate for genital ulcers at Week 12 for subjects who had genital ulcers at baseline | 9 |
| Proportion of subjects with no oral ulcers following complete response, ie, the first time when a subject has a complete response, during the Placebo-controlled Treatment Phase | 10 |
| Time to recurrence of oral ulcers following loss of complete response, ie, the first instance when a subject has a reappearance of oral ulcers following a complete response, during the Placebo-controlled Treatment Phase | 11 |
| Number of oral ulcers following loss of complete response, ie, the first instance when a subject has a reappearance of oral ulcers following a complete response, during the Placebo-controlled Treatment Phase | 12 |
| Change from baseline in the total score of the Static Physician's Global Assessment (PGA) of skin lesions (acne-like lesions, folliculitis and erythema nodosum) of BD at Week 12 in subjects who had BD skin lesions at baseline | 13 |
| Change from baseline in the pain of genital ulcers as measured by VAS at Week 12 in subjects who had genital ulcers at baseline | 14 |

For example, formal comparison with respect to the first secondary endpoint to be tested (Change from baseline in the pain of oral ulcers as measured by VAS at Week 12) will be conducted conditional on the test results for primary efficacy endpoint. If the test of AUC is

statistically significant, (i.e., two sided p-value ≤ 0.05), then the comparison for change from baseline in the pain of oral ulcers as measured by VAS at Week 12 will be performed at $\alpha = 0.05$. If the test result of AUC is not statistically significant, the formal statistical tests will not be performed for change from baseline in the pain of oral ulcers as measured by VAS at Week 12 and for the remaining of secondary endpoints.

For planned statistical tests that are not formally performed as a result of aforementioned multiplicity adjustment strategy, nominal 2-sided p-values (without adjustment for multiplicity) will still be computed as a measure of the strength of the association between the endpoints and the treatment effect rather than formal test of hypotheses. In addition, nominal 2-sided p-values may also be computed for other efficacy analysis.

10.2.2. Analysis of Primary Efficacy Endpoint

The primary efficacy endpoint is the AUC for the number of oral ulcers from Day 1 through Week 12/Day 85 (AUC₈₅). The AUC₈₅ will be compared between the placebo and APR 30 BID groups using a two-tailed parametric ANCOVA test at the 0.05 level. The model will include AUC₈₅ as the response variable; treatment, sex and region as factors; and the number of oral ulcers at baseline as a covariate. Within-group least-squares (LS) means, the associated standard errors (SE), and treatment differences in LS means, the associated SE, and associated 2-sided 95% CIs and 2-sided p-values will be derived from the model. The primary efficacy analysis will be performed using the ITT and PP population.

To derive AUC₈₅, the multiple imputation (MI) method will be used to impute missing oral ulcer counts on study visits from Day 1 through Week 12 with 3 steps:

- Check missing data patterns;
- If there are non-monotone patterns, then use the Markov Chain Monte Carlo (MCMC) with a single chain method to impute sufficient missing oral ulcer counts by treatment to make 25 data sets having monotone patterns only. The seed will be set to 37851. When the imputed oral ulcer count post-baseline is negative, the value of 0 will be assigned.
- For the monotone datasets, use the predictive mean matching method with treatment, sex, region, and oral ulcer counts from previous visits as covariate to impute the remaining missing oral ulcer counts to make datasets complete. The MONOTONE REGPMM statement will be used with a seed of 37951.

In this MI approach, instead of filling in a single value for each missing value, SAS® procedure PROC MI performs MI by replacing each missing value with a set of plausible values. The missing data will be filled in multiple times to generate multiple complete data sets. A supportive analysis based on PP population will be performed using MI approach with the same seed number on PP population.

Missing data patterns will be provided in a separate table. The results obtained from parametric ANCOVA models (one for each imputation) will then be combined to derive valid statistical inference through the SAS® procedure PROC MIANALYZE. The complete-data degrees of freedom for parameter estimate specified in the PROC MIANALYZE option will be pulled from degree of freedom from parametric ANCOVA models.

Parametric ANCOVA modeling AUC₈₅ will also be performed for ITT and PP populations using an LOCF approach, and for subjects who complete Week 12 assessment based on observed data as sensitivity analyses.

Additional sensitivity analyses for AUC₈₅ will be conducted for ITT population for subjects who complete each scheduled assessment from baseline through Week 12 based on observed data and for subjects who missed at most 2 scheduled oral ulcer assessments from baseline through Week 12 based on MI imputed data.

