## **8.4. Method of Treatment Assignment**

### **8.4.1. Placebo-controlled Treatment Phase (12 Weeks)**

At Visit 2, subjects who meet entry criteria will be randomized using a permuted block randomization in parallel 1:1 to receive either APR 30 BID or placebo, using a centralized IRT. Eligible subjects will be stratified according to gender, history of uveitis, and region (Japan and Other). The detailed information is documented in the IRT (IVRS) System Requirements document.

Designated research personnel at the investigational sites will be assigned password protected, coded identification numbers, which give them authorization to enter the IRT to randomize subjects. The system will present a menu of questions by which the research center personnel will identify the subject and confirm eligibility. When all questions have been answered, the IRT will assign a randomization identification number. Confirmation of the randomization will be sent to the investigational site, Celgene, and/or its representative.

During the study visits, the pharmacy or authorized study personnel at the investigational site will dispense coded IP kits in accordance with the randomization number assigned by the IRT.

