#### **10.6.1.2. Primary Analysis for Primary Efficacy Endpoint**

The primary efficacy endpoint is the AUC for the number of oral ulcers from Day 1 through Week 12. It will be compared between the placebo and APR 30 BID groups using an analysis of covariance (ANCOVA) model with the AUC as the response variable, the treatment, gender and region as factors, and the number of oral ulcers at baseline as a covariate. Multiple imputation method will be used to impute missing oral ulcer counts when the AUC is derived.

Sensitivity analyses including missing data imputations conducted for the primary efficacy endpoint to assess the robustness of the primary analysis will be detailed in the SAP.

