4.3. Stratification, Randomization, and Blinding

At Visit 2, subjects who meet entry criteria will be randomized using a permuted block randomization in parallel 1:1 (102 subjects per group) to receive either APR 30 BID or identically-appearing placebo BID for the 12-week Placebo-controlled Treatment Phase, using a centralized Interactive Response Technology (IRT). Eligible subjects will be stratified according to sex, history of uveitis, and region (Japan and Other).

This study will be conducted as a double-blind study for the Placebo-controlled Treatment Phase. During the Active Treatment Phase (Weeks 12 to 64), the IP will remain blinded, to prevent study personnel and subjects from knowing the IP assignment in the Placebo-controlled Phase.

To maintain the blind regarding the initial treatment assignment, all subjects will receive dose titration cards at Visit 9. Although only subjects initially randomized to placebo will be dose titrated during their first week of the Active Treatment Phase, all subjects entering the Active Treatment Phase will receive identically-appearing titration/treatment cards.

Data analyses and reporting will be performed after all subjects have completed Week 12/Visit 9 or have discontinued early (the 12-week database). After medical/scientific review has been completed, protocol violations/deviations have been identified, and the data have been declared final and complete, the 12-week database will be extracted and restricted with the corresponding external data files in the appropriate location in the data repository. For 12-week database lock, Celgene personnel who have access to the unblinded data are not to discuss or make materials available that would unblind individual subjects data to the personnel involved in the study conduct. Blinding to treatment assignment will be maintained at all study sites prior to the Week 68 database lock.

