The number of oral ulcers following subject's first loss of a complete response will be summarized for subjects who have a complete response prior to Week 12. The number of oral ulcers will be summarized as zero for subjects who had no reappearance of oral ulcers following a complete response prior to Week 12. The comparison between two treatment groups will be performed using ANCOVA model with the treatment, sex and region as factors and baseline number of oral ulcers as a covariate. Within-group LS means, the associated SEs, and treatment differences in LS means, the associated SE, and associated 2-sided 95% CIs and 2-sided p-values will be derived from the model. The treatment comparison will only be conducted if appropriate.

The summary tables with descriptive statistics for number of oral ulcers and general ulcers will be presented by treatment group at all applicable analysis visits.

Summary tables for change from baseline with descriptive statistics will be presented for continuous variables including pain VAS of oral ulcers, pain VAS of genital ulcers, BD Current Activity Form Scores, BD QoL scores, BSAS scores,

, and total score of the Static PGA of skin lesions by treatment group at all applicable visits per study period. For the PGA, only subjects who had BD skin lesions at baseline will be included. For the pain VAS of genital ulcers, only subjects who had genital ulcers at baseline will be included.

The LOCF approach will be used to impute the missing assessment at Week 12 for the following endpoints: pain VAS of oral ulcers, pain VAS of genital ulcers, BD Current Activity Form Scores, BD QoL, and BSAS. The change from baseline at Week 12 (LOCF approach) will be compared between the placebo and the APR 30 BID group using ANCOVA model with change from baseline at Week 12 as the response variable, treatment, sex and region as factors and baseline value as a covariate. Within-group LS means, the associated SEs, and treatment differences in LS means, the associated SE, and associated 2-sided 95% CIs and 2-sided p-values will be derived from the model. A sensitivity analysis for change from baseline in the pain VAS of oral ulcers at Week 12 will be conducted using mixed-effects model for repeated measures (MMRM) with treatment, visit, treatment-by-visit interaction, sex and region as factors and baseline value as a covariate. An unstructured covariance matrix that is homogeneous across treatment groups is to be used.

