10.4. Subgroup Analysis

The focus of subgroup analyses will be limited to the stratification factor and baseline characteristics as listed below and will be conducted on the ITT population for AUC₈₅:

- Sex (male, female)
- Race (White, non-White)
- Age (< 40, \geq 40 to < 65, \geq 65 years years)
- Region (Japan, Other; Europe, North America, Asia, Rest of the World)
- Baseline weight category (< 50, \geq 50 to < 60, \geq 60 to < 70, \geq 70 to < 85, \geq 85 kg)
- Baseline BMI category (< 18.5, \geq 18.5 to < 25, 25 to < 30, \geq 30 kg/m²)
- Alcoholic beverage intake (yes, no)
- Tobacco use (current user, past user, never user).
- Duration of disease (\leq 2, > 2 to \leq 6, > 6 to \leq 10, > 10 years)
- Baseline oral ulcers category (\geq 2 to \leq 5, > 5 to \leq 10, \geq 10)
- Prior use of colchicines (Yes, No)
- Prior use of oral corticosteroids (Yes, No)

The consistency of the treatment effect across subgroups will be assessed in the context of the primary methods used for the analyses. For AUC₈₅, sex or region will not be included as a factor for the sex or region subgroup analysis, respectively, in the ANCOVA model.

Forest plots will be provided based on the treatment differences for each subgroup estimated as described above for AUC₈₅.

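### History of uveitis stratifies the randomisation but is left out of the primary ANCOVA and related models; adding it is a small, nearly free improvement

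*SAP*

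**What the plan says.** Both documents name three stratification factors. SAP 4.3: "Eligible subjects will be stratified according to sex, history of uveitis, and region (Japan and Other". Protocol 8.4.1 says the same: "Eligible subjects will be stratified according to gender, history of uveitis, and region (Japan and Other".

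The models carry two of the three:

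- Primary ANCOVA, protocol 10.6.1.2: "the treatment, gender and region as factors, and the number of oral ulcers at baseline as a covariate". SAP 10.2.2 repeats it: "treatment, sex and region as factors; and the number of oral ulcers at baseline as a covariate".
- Second imputation step, SAP 10.2.2: "use the predictive mean matching method with treatment, sex, region, and oral ulcer counts from previous visits as covariate".
- Change-from-baseline ANCOVAs, SAP 10.2.3: "treatment, sex and region as factors and baseline value as a covariate".
- MMRM sensitivity analysis for oral ulcer pain, SAP 10.2.3: "treatment, visit, treatment-by-visit interaction, sex and region as factors and baseline value as a covariate".

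SAP 10.4 introduces the subgroups with "The focus of subgroup analyses will be limited to the stratification factor and baseline characteristics as listed below", and the list that follows has sex and region but not history of uveitis. The sensitivity analyses of the primary endpoint change the missing-data handling or the set of subjects, never the model terms. SAP 8.2 does tabulate history of uveitis at baseline, from the IRT and, separately, from clinical data, so the variable is in hand. SAP section 14 declares no change from the protocol's statistical section.

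**The concern.** The usual practice is to analyse as randomised: a factor important enough to stratify on goes into the model unless there is a reason to drop it. Here one of three is dropped without a stated reason.

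Stratified blocks balance the factor between arms, so whatever variance it explains no longer contributes to the sampling variance of the treatment estimate. A model without the factor still counts that variance as residual. If the factor is prognostic given baseline count, sex and region, the reported SE exceeds the true one, the confidence interval is too wide and the actual type I error falls below 5%. What is at stake is therefore a little precision. Bias, false-positive risk and the credibility of a positive result are not affected.

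The same model also serves the ANCOVAs on all ITT subjects at ranks 2, 3, 4 and 8 of SAP Table 4, in a fixed sequence that stops at the first failure.

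**Working it through.** **Inputs from the documents.** SAP 4.4 and protocol 10.3: difference 66, SD 144, 102 per group, two-sided 0.05, power 90%. The planned ANCOVA has 5 parameters (intercept, treatment, sex, region, baseline count), so residual df = 204 − 5 = 199, or 198 with uveitis added.

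**Inputs assumed.** The documents give neither the prevalence of uveitis history nor its prognostic strength. R² is the share of the planned model's residual variance that it explains. Prevalence p is taken as 30%, with a range of 20% to 50%.

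**1. The plan's own figure.** SE = 144 × √(2/102) = 20.16. Power is 90.5% by the normal approximation and 90.3% by the noncentral t, which needs 102 per group. The stated 90% is reproduced.

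**2. Plausible R².** A gap in mean AUC between subjects with and without uveitis history corresponds to R² through gap = SD × √(R² / (p(1 − p))), here with SD 144:

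| R² | p = 20% | p = 30% | p = 50% |
|---|---|---|---|
| 1% | 36 | 31 | 29 |
| 2% | 51 | 44 | 41 |
| 5% | 81 | 70 | 64 |

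An R² of 5% would need a gap about as large as the planned drug effect of 66. The case therefore rests on 1% to 2%.

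**3. Effect of leaving the factor out.** Reported SE without the factor: SE_rep = SD × √(2/102). True SE under stratified randomisation: SE_true = SE_rep × √(1 − R²).

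- Power without the factor: noncentral t, 199 df, noncentrality 66/SE_true, critical value 1.972 × SE_rep/SE_true.
- Power with the factor: noncentral t, 198 df, same noncentrality, critical value 1.972.
- Type I error without the factor: two-sided tail of t (199 df) beyond 1.972 × SE_rep/SE_true.
- Half-width of the 95% CI: 1.972 × SE.

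With 144 as the residual SD:

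| R² | SE_rep | SE_true | Power without | Power with | Gain (points) | Half-width without / with | Type I error without |
|---|---|---|---|---|---|---|---|
| 0 | 20.16 | 20.16 | 90.27% | 90.27% | −0.001 | 39.8 / 39.8 | 0.050 |
| 1% | 20.16 | 20.06 | 90.39% | 90.55% | 0.17 | 39.8 / 39.6 | 0.049 |
| 2% | 20.16 | 19.96 | 90.50% | 90.83% | 0.33 | 39.8 / 39.4 | 0.048 |

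**4. A smaller residual SD.** The 144 belongs to an unadjusted t-test. If baseline count, sex and region explain an assumed 20% of variance, the residual SD is 144 × √0.8 = 128.8 and SE_rep is 18.04. Power without and with the factor is then 95.45% and 95.54% at R² = 1% (gain 0.09), and 95.53% and 95.72% at R² = 2% (gain 0.19).

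**5. Simulation.** 20,000 trials per scenario were run with 204 subjects, permuted blocks of 4 in 8 strata, and assumed shares of 30% uveitis history, 40% male and 20% Japan. At a gap of 44, the mean reported SE was 20.19 without the factor and 19.99 with it, while the sampling SD of the estimate was 20.06 and 20.05. The estimate itself barely changes; the reported SE comes down to match its true spread. Type I error was 0.048 without and 0.050 with the factor, and power 0.904 and 0.907 (Monte Carlo SE about 0.0015 and 0.002).

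**The case against.** The best defence is that nothing here is invalid. Protocol and SAP specify the same primary model, so there is no contradiction and no late choice. Omitting a stratum that may not be prognostic is conservative. Whether uveitis history predicts oral ulcer AUC is unknown, and at R² = 0 there is no gain. Several of the simulated power differences (for example 0.902 against 0.903 at a gap of 30) are no larger than the quoted Monte Carlo SE. The change would also create a departure from the protocol where none exists, and would split one ANCOVA specification, because the same SAP paragraph covers genital ulcer pain in a subset.

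Most of this stands as a limit on importance. The gain is conditional and small, and this is not a validity flaw. It does not remove the point: the omission is unexplained, the value is already collected, and the cost if the factor proves useless is one degree of freedom. The size of the gain rests on the analytic calculation, not on the simulated power differences.

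Two reservations about the documents also stand. SAP 10.2.3 calls the log-rank and Cox analyses stratified without naming the strata, and its CMH wording names sex and region as examples, so uveitis history is not ruled out there. Parts of the SAP are redacted or missing, so the absence of a reason can be asserted only for the text available.

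**Conclusion.** The concern holds, as a minor efficiency point. History of uveitis is a randomisation factor and is missing from the primary ANCOVA, the secondary ANCOVAs on all ITT subjects, the MMRM and the predictive mean matching step. At an assumed R² of 1% to 2%, adding it gains 0.09 to 0.33 power points and, with SD 144, takes 0.2 to 0.4 AUC units off a 95% CI half-width of 39.8. At R² = 0 it costs about 0.001 points. Without it, type I error is at or just below 0.05, and the 90% power claim is sound. The size depends on a prognostic strength that the documents do not give. The change is worth making because it costs almost nothing.

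**What to change.** Before the 12-week database lock:

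- Add history of uveitis, IRT value (the one used to randomise), as a main-effect factor in the primary ANCOVA, in the secondary ANCOVAs on all ITT subjects (Table 4 ranks 2, 3, 4 and 8) and in the MMRM. ANCOVAs on subsets can keep the present model, since uveitis cells may be sparse there; the SAP should say so.
- Add it as a covariate in the monotone predictive mean matching step, so that this step still contains every ANCOVA term. The MCMC step is run by treatment and names neither sex nor region, so it can stay as it is.
- Declare the change from protocol 10.6.1.2 in SAP section 14.
- If the protocol model must remain primary, pre-specify the three-factor ANCOVA in SAP 10.2.2 as a sensitivity analysis.
- As a clarification, name the strata for the CMH, log-rank and Cox analyses. Sex and region alone is defensible: with the shares assumed in the simulation, the two smallest of 8 strata would hold 204 × 0.3 × 0.4 × 0.2 = 4.9 and 204 × 0.3 × 0.6 × 0.2 = 7.3 subjects, against 204 × 0.4 × 0.2 = 16.3 in the smallest of 4. With uveitis history at 20% to 50% and Japan at 10% to 30%, the 4.9 ranges from 1.6 to 12.2.

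The cost is one degree of freedom in the ANCOVA (199 to 198) and a few sentences of SAP text. No new data are needed.
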